The improvement in neurodevelopmental outcome we reported was primarily due to a decrease in the risk of *cognitive* impairment, measured with the Bayley scales of Infant Development, a standardized tool for assessing neurodevelopmental outcome in this age group. As mentioned above, the initial hypothesis of the study was that iNO therapy would decrease the incidence of death and chronic lung disease. However, we found that the beneficial effect of iNO therapy on neurodevelopment was independent of important clinical factors known to affect neurodevelopmental outcome, including whether infants had chronic lung disease. Furthermore, the magnitude of improvement in neurodevelopmental outcome persisted after statistical adjustment for the presence and absence of intraventricular brain hemorrhage or periventricular leukomalacia (PVL, a softening of the white matter of the brain, due to reduced blood flow). Therefore, iNO therapy appears to be directly neuroprotective in ventilated, preterm infants. The number of children in each group having cerebral palsy, motor delay, blindness, or deafness did not differ between iNO- and placebo-treated infants.

Advances in neonatal intensive care medicine notwithstanding, we have not successfully developed neuroprotective therapies for these at risk preterm infants; iNO therapy, therefore, constitutes the first

intervention to allow the preterm brain to develop normally outside the womb. In our previous study, we treated babies for one week regardless of their level of prematurity. However, we do not know what duration of treatment will result in maximum neuroprotection, and will give the best neurodevelopmental outcome to the most infants. It is likely that maximal benefit of iNO therapy will occur with longer treatment, throughout the preterm period. *Our goal, therefore, is to determine whether iNO therapy given during throughout the preterm period results in further improved neurodevelopmental outcomes, and to understand the biological relationships between iNO treatment and neurodevelopmental outcome.* To achieve this goal, we propose performing a randomized, placebo-controlled, double-blind study of the effect of iNO therapy with gestational age-determined treatment length on neurodevelopmental and growth outcomes of preterm infants. Our Specific Aims are:

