**Specific Aim #1. Determine the effectiveness of iNO therapy on improving neurodevelopmental outcome in all O2-dependent premature infants having birth weights < 1500g.** We hypothesize that iNO therapy will improve neurodevelopmental outcome and growth at 18 months postconceptional age compared with placebo treated infants. In a double-blind, placebo-controlled clinical trial, premature infants being cared for in the Intensive Care Nursery at the University of Chicago Medical Center requiring any level of respiratory support will be randomized to receive iNO or placebo gas. Treatment will continue until infants either no longer require supplemental O2 therapy or reach 33 weeks gestational age, whichever comes first. At 18 months postconceptional age, infants will have neurodevelopment assessed and secondary clinical outcomes measured. The relative risks of abnormal neurodevelopmental outcome in the two groups will be compared. The roles played by variables known to independently affect neurodevelopmental outcome, as well as variables known to mediate abnormal neurodevelopmental outcomes will be statistically assessed.

**Specific Aim #2. Assess the mechanisms by which iNO therapy alters neurodevelopmental outcome in preterm infants.** We hypothesize that the amount of nitric oxide delivery to tissues will be positively correlated with neurodevelopmental outcome. Using routinely collected arterial and venous blood from infants in this study, measurements of nitrosylated hemoglobin and nitrite will be made. Arterial-venous differences will be calculated and mean differences compared across treatment groups. Arterial venous

differences will be regressed against neurodevelopmental outcome. Plasma levels of cyclic guanosine monophosphate (cGMP), the intracellular second messenger induced by nitric oxide will also be measured and levels regressed against neurodevelopmental outcome.

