## **RESEARCH PLAN**

**Overall Experimental Plan:** The study is a single-site, randomized, double-blind, placebo-controlled trial of inhaled nitric oxide therapy in all preterm infants with any respiratory disease who weigh <1500g at birth. The trial is designed to treat these infants with nitric oxide from birth to 33 weeks gestation – a critical period of brain development in preterm infants. Our primary objective is to compare neurodevelopmental outcomes between our iNO and placebo-treated patients. We also wish to study the mechanisms underlying the protective effect of iNO, by assessing the relationship between nitric oxide delivery to tissues and neurodevelopmental outcome.

The major differences between this study and our previous study are:

- 1) Inclusion of all preterm infants requiring at least supplemental oxygen therapy. Approximately half of all infants weighing <1500 at birth do not require mechanical ventilation with a breathing machine, which was one criterion for inclusion in our previous study. However, these infants are still at risks for abnormal neurodevelopmental outcomes. By including all infants requiring at least supplemental oxygen by nasal cannula, we hope to obtain information regarding the potential beneficial effects of iNO applicable to the majority of at-risk preterm infants.
- 2) Gestational age-dependent duration of iNO therapy. In our previous study, infants were treated with iNO or placebo for 7 days (if still on mechanical ventilation). Consequently, infants received iNO therapy during different periods of brain development: for example, infants of 24 weeks gestation (16 weeks early) received iNO during a period during brain cells were being rapidly produced, while infants of 30 week's gestation received iNO after brain cells had been made and were now forming connections. In this study, our goal is to provide iNO during the entire time the premature brain is developing outside the womb. Therefore, infants will be treated from birth until 33 weeks gestation, so that less mature infants will be treated for a longer time.

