- 3) Specific design of the study to assess neurodevelopmental outcome. Our previous study had been designed to assess the effect of iNO treatment on the incidence of chronic lung disease and death; we assessed these infants' neurodevelopmental outcomes because of our unanticipated finding of decreased brain bleeding and softening. This study has as its primary outcome the incidence of abnormal neurodevelopmental outcome.
- 4) Laboratory-based Specific Aim to assess the mechanisms of the iNO-induced neuroprotection.

**Specific Aim #1. Assess the role of iNO therapy on neurodevelopmental outcome in all oxygen-dependent premature infants having birth weights < 1500g.**

(i) *Rationale.* We have previously found that brief (1 week) treatment of ventilated preterm infants reduces abnormal neurodevelopmental outcome. Because brain development continues throughout gestation, we hypothesize that iNO therapy will be protective to the preterm brain if given from birth until the risk for abnormal neurodevelopmental outcome is similar to that of term infants.

(ii) *Study design.* We have designed a randomized, placebo controlled, double blind study of iNO therapy during Intensive Care Nursery stay, followed by blinded neurodevelopmental assessment at 18 months corrected age, a commonly used developmental endpoint.

(iii) *Patients.* All premature infants cared for in the Intensive Care Nursery at the University of Chicago Medical Center, who are less than 72 hours old, weighing less than 1500 grams at birth, and requiring any respiratory support, will be eligible for the study. Enrolled infants are anticipated to have the same demographics as we have previously reported: 52% male, 70% African-American, 45% single parent household. Potential subjects will be identified and informed consent sought, if possible, prior to birth, otherwise, within the first 3 days after birth.

(iv) *Exclusion criteria.* Those infants with severe congenital anomalies, including major congenital heart disease, or major kidney, lung or brain malformations will be excluded, as will be those infants with a genetic syndrome. Infants judged by the physician to not be viable will be excluded from the study, as will extremely sick infants requiring very high ventilatory pressures (Oxygen Index  $\geq 20$ ). This latter group is excluded because of a previous study by Van Meurs which showed that infants in this category are made worse by inhaled nitric oxide.

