(v) *Patient randomization.* Randomization will be performed as we have previously published. To keep birth-weight distribution comparable in the two groups, we will use five 250-gram-birth weight strata for randomization. To ensure equal enrollment in the two groups, infants will be randomly assigned within each stratum, according to a permuted block design to receive inhaled nitric oxide (INOmax®, INO Therapeutics) or

oxygen placebo. This strategy provides a balanced group assignment with every 4 enrollments.

(vi) *Patient enrollment at study entry procedures.* We will enroll patients and enter them into the study as we have previously published. Briefly, potential subjects will be identified, prenatally if possible, and the parents approached for informed consent. With consent obtained, and the infant born, admitted, and verified to meet inclusion criteria, a sealed envelope containing the randomized treatment assignment, appropriate identifying labels, etc., will be pulled and opened by the respiratory therapist. Documentation of the treatment assignment and patient data will be recorded by the respiratory therapist in the study book (kept in the respiratory therapy room), and an INOvent® brought to the bedside. The INOvent will be set to deliver either iNO or oxygen according to the treatment randomization and then covered to conceal the treatment group from the caregivers and investigators.

(vii) *Treatment.* iNO or placebo (oxygen) will be given 5 ppm while ventilated or on continuous positive airway pressure (CPAP) and 10 ppm while on nasal cannula oxygen. In infants receiving iNO by nasal cannula, iNO concentrations are set to 10 ppm, because previous studies have shown that delivery 10 ppm by nasal cannula results in nasopharyngeal concentrations of about 5 ppm^9. These dosages will continue until the infant no longer needs supplemental oxygen or reaches 33 weeks post conceptional age. All infants will have iNO delivery devices (INOvents) at the bedside to deliver either iNO or O2, and will be shrouded to hide from caregivers the nature of the gas being delivered. Only respiratory therapy and data safety monitor to know of gas assignments.

(viii) *Data Collection.* Clinical data (fluids, medications, diagnoses, ventilator settings) will be collected daily by our research professional.

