(ix) *Sample size.* In our previous study of infants with RDS, iNO treatment cut the risk of abnormal neurodevelopmental outcome by half. The baseline incidence of abnormal neurodevelopmental outcome is 40% in this age group by published NICHD data. Therefore to see a decrease of abnormal neurodevelopmental outcome to 20% (half of baseline incidence) with 80% power, 82 babies are needed in each arm of the study, for a total of 164 babies. We have previously published an overall mortality rate for intubated infants < 2000g in our nursery of 23%. Because we are including non-intubated infants, we

estimate a mortality rate of about 18%. Therefore, to ensure sufficient infants surviving to follow up, we anticipate needing to enroll approximately 215 babies over 18 months. With a historic 80% follow-up rate, we will need a total of 268 infants. Every year we admit approximately 175-200 infants with birth weights < 1500g. We therefore anticipate enrollment taking as long as 18 months. Our non-consent rate historically is < 10%.

(x) *Standards of neonatal intensive care.* Because we have shown no effect of ventilatory strategy on neurodevelopmental outcome, there will be no external control of ventilatory modality. Because this is a single-site study, variability in practice exists only between our eight member group of neonatologists, with constant care provided by nurse practitioners, residents, and nursing staff.

(xi) *Safety monitoring.* As per our clinical routine, methemoglobin is regularly monitored with arterial blood gases. Although we and others have shown that iNO therapy is safely used in preterm infants, interim safety analyses will be performed when 50% of patients enrolled. Deaths will be compared, as will the incidence of severe intraventricular hemorrhage, and tests of significance made with Chi-square. The study will be stopped if the incidence of either index in the iNO groups is significantly higher than in placebo groups.

(xii) *Primary Outcome.* As we have published, we will measure abnormal neurodevelopmental outcome at 18 months corrected age. Three disability levels will be assessed: disability (cerebral palsy, blind in both eyes, or deaf in both ears); delay (score on Mental or Psychomotor Developmental Index of the Bayley Scales of Infant Development < 70 without a disability) or normal (without disability or delay).

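### Entry has no upper gestational-age limit although study gas stops at 33 weeks, so an infant with no planned exposure can be randomised (minor; one added criterion)

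*Combined protocol and SAP*

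**What the plan says.** **Entry.** Specific Aim #1 (iii) Patients takes premature infants less than 72 hours old, "weighing less than 1500 grams at birth, and requiring any respiratory support, will be eligible for the study". Prematurity is not defined in weeks. Consent is sought before birth if possible, "otherwise, within the first 3 days after birth". Section (iv) excludes severe anomalies, genetic syndromes, non-viable infants and an Oxygen Index of 20 or more. It says nothing about gestational age.

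**Stop rule.** The Specific Aims end treatment when infants no longer need supplemental oxygen or "reach 33 weeks gestational age, whichever comes first". Section (vii) Treatment says: "These dosages will continue until the infant no longer needs supplemental oxygen or reaches 33 weeks post conceptional age". The first text counts gestational age and the second post-conceptional age.

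**Intent.** Item 2 of the differences from the previous study says that "infants will be treated from birth until 33 weeks gestation, so that less mature infants will be treated for a longer time".

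**Order of steps.** In (vi) the infant is "verified to meet inclusion criteria, a sealed envelope containing the randomized treatment assignment" then being opened by the respiratory therapist.

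**Analysis and size.** Section (xvi) analyses by intent to treat. Section (ix) plans 40% against 20% abnormal outcome, 80% power and 82 infants per arm. After mortality it concludes: "With a historic 80% follow-up rate, we will need a total of 268 infants".

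**The concern.** The stop rule depends on gestational age and the entry rule does not, so the two can conflict. An infant can satisfy every entry criterion while the age condition that ends treatment is already met. Two kinds of infant are affected:

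- a growth-restricted premature infant under 1500 g born at or after 33 weeks;
- an infant born a few days before 33 weeks who passes that age before randomisation, because entry is allowed up to 72 hours after birth.

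Neither has any study gas planned, in either arm. Intent to treat keeps both in the comparison, where they cannot contribute a treatment difference. They pull the relative risk toward 1 and cost some power. The protocol also does not tell the respiratory therapist what to do when an envelope is opened for such an infant.

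**Working it through.** **1. Does the text permit it?** For an infant of 1400 g born at 33 weeks 2 days, premature, on nasal cannula oxygen and 10 hours old, each condition in (iii) is met and no exclusion in (iv) applies. The 33-week stop in the Specific Aims is already met. No other section supplies an upper gestational age, and the randomisation strata in (v) use birth weight only.

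**2. Late entry.** On the scale of gestational age at birth plus postnatal age, 32 weeks 5 days + 48 hours = 33 weeks 0 days. With entry allowed to just under 72 hours, births from about 32 weeks 4 days to 32 weeks 6 days can reach the stop before randomisation. This step assumes that both age terms in the stop rule mean that scale.

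**3. Reproduce the plan's sample size.** Inputs from (ix): 40% against 20%, power 80%. Alpha and sidedness are not stated there; two-sided 0.05 is assumed. With mean risk 0.30:

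n = [1.96√(2 × 0.30 × 0.70) + 0.842√(0.40 × 0.60 + 0.20 × 0.80)]² / 0.20² = 81.2, so 82 per arm. This matches the plan. Power at 82 is 80.4%.

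**4. Evaluable infants at planned enrolment.** With 18% mortality and 80% follow-up from (ix): 268 × 0.82 × 0.80 = 176, or 88 per arm.

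**5. Dilution.** Let f be the unexposed share, an assumption. Power = Φ{[|p1 − p2|√n − 1.96√(2p̄(1 − p̄))] / √[p1(1 − p1) + p2(1 − p2)]}, where p̄ is the mean of p1 and p2.

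- Case A, unexposed infants have 40% risk in both arms: 0.40 against 0.20 + 0.20f.
- Case B, they have 20% risk in both arms: 0.40 − 0.20f against 0.20. Background section 1 supports a lower risk in more mature infants, but the 20% is assumed.

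| f | Infants of 176 | Power kept, A | Power kept, B | Power if excluded, not replaced | Gain, A | Gain, B | Expected relative risk if kept (B to A) |
|---|---|---|---|---|---|---|---|
| 0 | 0 | 83.1% | 83.1% | 83.1% | – | – | 0.50 |
| 1% | about 2 | 82.3% | 82.4% | 82.7% (n = 88 × 0.99 = 87.12) | 0.5 | 0.3 | 0.503 to 0.505 |
| 3% | about 5 | 80.5% | 81.0% | 81.9% (n = 88 × 0.97 = 85.36) | 1.4 | 1.0 | 0.508 to 0.515 |

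Gains are in percentage points, taken from unrounded power. Power at 88 per arm reaches 80% at f = 3.55% in case A and 4.27% in case B. At the plan's own 82 per arm there is little slack: 80.4% becomes 79.5% to 79.6% at 1% and 77.6% to 78.1% at 3%.

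**6. False-positive risk.** Unexposed infants have the same expected risk in both arms whether or not the gas works, so they create no spurious difference.

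**7. Enrolment time.** From (ix), 175 to 200 admissions a year, with non-consent at its 10% upper bound, before other exclusions: 268 / (200 × 0.9) × 12 = 17.9 months and 268 / (175 × 0.9) × 12 = 20.4 months. Dividing by 0.99 gives 18.0 to 20.6 months (about 0.2 more). Dividing by 0.97 gives 18.4 to 21.1 months (about 0.6 more).

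**The case against.** The strongest reply is that the intended population is clear. The plan describes treatment from birth to 33 weeks, and an infant born at or after 33 weeks cannot be treated that way. Staff would have to seek consent, open an envelope and bring a device to the bedside for an infant with no gas due. That may make the event rare. It does not remove it, because a statement of treatment duration excludes nobody.

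The second reply is about the age scale. If post-conceptional age in (vii) is read literally, from conception, the stop falls about two weeks later than in the Specific Aims, and the infant born at 32 weeks 5 days does have planned exposure. This stands as a condition on the late-entry example. On that reading the mismatch moves to infants born about two weeks later, but it does not close.

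Third, very short exposure is built into the design, since gas also stops when oxygen is no longer needed. An infant at 32 weeks 6 days would be kept and probably dilutes almost as much as one at 33 weeks 0 days. This is true and is a reason to keep the point small. The proposed limit removes only infants whose planned exposure is nil on the day of entry.

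A reader might also infer more than the text supports:

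- That entry has no age limit at all. It has one, but it is postnatal (under 72 hours) and does nothing to align entry with a gestational stop.
- That the previous study shows how the gap arose. The plan says "In our previous study, we treated babies for one week regardless of their level of prematurity", which shows that the earlier treatment length did not depend on age. It does not show what that study's entry rule was, and the cited publication is not available here.

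**Conclusion.** The mismatch between the entry rule and the stop rule is real and follows from the text, but it is minor. At an assumed unexposed share of 1% to 3%, excluding these infants without replacement gains about 0.3 to 1.4 points of power. Keeping them moves the expected relative risk from 0.50 to no more than 0.515. At planned enrolment, power stays at or above 80% up to a share of about 3.5%.

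These figures rest on four assumptions: the share itself, which the documents do not give; two-sided 0.05; no effect in unexposed infants; and a risk of 20% or 40% in them. The late-entry group rests further on reading both age terms as gestational age at birth plus postnatal age.

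A reader might conclude that the trial is underpowered for this reason. A 10% share at 82 per arm would indeed give 70.6% in case A, but nothing in the documents supports a share of that size, and the 1500 g limit points to a small one. This is a cheap improvement, not a threat to the result.

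**What to change.** Add to (iii): *gestational age at birth plus postnatal age below 33 weeks 0 days at randomisation*. Use the same age scale for the stop rule in the Specific Aims and in (vii), replacing the two differing terms. Check the criterion at the existing verification step in (vi), before the envelope is opened.

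The limit belongs at randomisation, not at birth, because a limit at birth would miss the infant who passes 33 weeks within the 72-hour window. The scale must be named: an unqualified age below 33 weeks could be read as postnatal age, which every eligible infant meets. The requirement for any respiratory support can stay as it is.

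The cost is one criterion and no new procedure. The downside is slightly fewer eligible infants, or about 0.2 to 0.6 months more enrolment if they are replaced. Even without replacement, power is higher than if they are kept.

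### The entry criterion (any respiratory support) is wider than the oxygen-dependent population the trial describes and does not match the oxygen-based stop rule for study gas

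*Combined protocol and SAP*

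**What the plan says.** All references are to the combined protocol and SAP.

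**Entry, wider wording.** Specific Aim #1 (iii) Patients says infants "weighing less than 1500 grams at birth, and requiring any respiratory support, will be eligible for the study". The Aim 1 paragraph under Specific Aims says infants "requiring any level of respiratory support will be randomized to receive iNO or placebo gas". The exclusion list in (iv) does not remove infants who need no oxygen.

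**Entry, narrower wording.** The Overall Experimental Plan lists as its first difference from the previous study "Inclusion of all preterm infants requiring at least supplemental oxygen therapy". The Aim 1 titles, under Specific Aims and in the Research Plan, also limit the population to oxygen-dependent infants.

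**Randomisation.** Under (vi), once the infant is "verified to meet inclusion criteria, a sealed envelope containing the randomized treatment assignment" is opened by the respiratory therapist.

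**Gas.** Under (vii), gas is "given 5 ppm while ventilated or on continuous positive airway pressure (CPAP) and 10 ppm while on nasal cannula oxygen". It continues until supplemental oxygen is no longer needed or 33 weeks is reached. The Specific Aims text gives the same rule: treatment ends when oxygen is no longer required "or reach 33 weeks gestational age, whichever comes first". Section (xvii) adds a wean of 1 ppm every 12 to 24 hours.

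**Analysis and size.** Section (xvi) specifies intent to treat. Section (ix) sizes the trial for a fall from 40% to 20%, with 80% power and 82 per arm. It inflates for death and loss to follow-up only.

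**The concern.** Entry depends on respiratory support and stopping depends on oxygen. These conditions differ for an infant on CPAP or a ventilator in room air. Such an infant satisfies the eligibility section, can have an envelope opened, and at that moment already satisfies the stop rule.

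The plan has room for such infants. It deliberately adds non-ventilated infants, noting that "Approximately half of all infants weighing <1500 at birth do not require mechanical ventilation with a breathing machine". Entry is open to 72 hours of age, so oxygen need can change before randomisation. Section (x) leaves the mode of support to the clinicians.

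Two things are at stake. First, who is enrolled depends on which sentence staff follow. Second, infants with little or no study gas stay in the arm to which they were randomised. That introduces no bias in the comparison of arms as randomised, but it pulls the difference towards zero, and the sample size assumes the full halving in every evaluable infant.

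**Working it through.** **1. Where the texts meet.** For an infant under 1500 g on CPAP in room air:

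| Section | Result for this infant |
|---|---|
| (iii) Patients; Specific Aims paragraph | Eligible |
| Overall Experimental Plan, difference 1; Aim 1 titles | Outside the population |
| (vii) dose sentence | 5 ppm, because on CPAP |
| (vii) and Specific Aims stop rule | Already at the stopping point |
| (xvii) wean | If started at 5 ppm, 5 steps of 12-24 h = 2.5 to 5 days |

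No section resolves the conflict.

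**2. Reproduce the plan's figure.** The documents state no alpha; two-sided 0.05 is assumed. With p1 = 0.40, p2 = 0.20 and mean p = 0.30:

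n = [1.96 × √(2 × 0.30 × 0.70) + 0.8416 × √(0.40 × 0.60 + 0.20 × 0.80)]² / 0.20² = 81.2, so 82 per arm.

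This matches section (ix). Power at 82 per arm is 80.4%.

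**3. Evaluable infants expected.** With 268 enrolled, 18% mortality and 80% follow-up, all from section (ix): 268 × 0.82 × 0.80 = 175.8, or about 88 per arm. The stated rates need only 164 / (0.82 × 0.80) = 250 enrolled, so 268 gives a small cushion. Power at 88 per arm without dilution is 83.1%.

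**4. Dilution, worst case.** Let f be the share of evaluable infants in each arm who were on support without oxygen at entry, with no treatment effect and their own abnormal-outcome rate u. Then:

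- placebo rate = (1 − f) × 0.40 + f × u
- iNO rate = (1 − f) × 0.20 + f × u

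The documents give neither f nor u. The range assumed for f is 0 to 20%. For u, 40% (the planning rate) and 20% (a lower-risk group) are shown.

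| f | Rates, u = 40% | Power at 88 | Rates, u = 20% | Power at 88 |
|---|---|---|---|---|
| 0% | 40.0 v 20.0 | 83.1% | 40.0 v 20.0 | 83.1% |
| 2% | 40.0 v 20.4 | 81.4% | 39.6 v 20.0 | 81.7% |
| 5% | 40.0 v 21.0 | 78.7% | 39.0 v 20.0 | 79.4% |
| 10% | 40.0 v 22.0 | 73.7% | 38.0 v 20.0 | 75.3% |
| 20% | 40.0 v 24.0 | 62.6% | 36.0 v 20.0 | 65.9% |

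**5. Partial exposure.** If these infants had half the relative reduction (iNO-arm rate 0.75 × u), power at 88 per arm would be about 81% at f = 5%, 78-79% at 10% and 72-74% at 20%.

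**6. Enrolment to hold 80% power in the worst case.** The need is 90-91, 99-103 or 123-133 evaluable per arm at 5%, 10% or 20%. Doubling and dividing by 0.82 × 0.80 = 0.656 gives about 274-277, 302-314 or 375-405 enrolled, against the planned 268.

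**The case against.** The strongest reply is that this is loose drafting and the intent is clear. The oxygen condition is stated as an inclusion feature in the Overall Experimental Plan, and section (iii) sits under a title naming oxygen-dependent infants. Specific Aim #2 (ii) expects infants born before 31 weeks to be treated beyond two weeks because they will still need respiratory support. That suggests the authors used oxygen need and respiratory support interchangeably and expected few early stops below 31 weeks. This stands as evidence of intent, and it makes a share as high as 20% look unlikely. It does not cure the defect: the criterion that staff verify before opening the envelope is the wider one.

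A reader might infer that the plan knowingly admits room-air infants. The documents do not support that, because they also carry the narrower definition.

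A reader might also infer that such infants would certainly receive no gas. That is only one reading. The dose sentence has no oxygen condition for starting, and the stop rule presupposes that gas has begun. With the wean, an infant could get several days of exposure. The previous study treated for at most 7 days and is credited in section (ix) with halving risk, so zero effect is a worst case.

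Finally, the share has no source in the documents. At 2%, power stays above 80% even in the worst case.

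**Conclusion.** The inconsistency is real: followed as written, the eligibility section can admit an infant who already meets the stop rule, and the plan does not say how that infant is treated. The consequence is possible dilution in an unbiased comparison.

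Its direction is known and its size is not. With zero effect in these infants, 88 evaluable per arm and two-sided alpha 0.05, the loss from 83% power is 1 to 2 points at a 2% share, about 4 at 5%, 8 to 9 at 10% and 17 to 21 at 20%. These are worst-case figures over an assumed range; they do not show that the trial is underpowered. The ambiguity about who is enrolled and how they are treated is reason enough to correct the wording, since the correction is so small.

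**What to change.** In section (iii) and the Aim 1 paragraph under Specific Aims, replace the entry condition with: requiring supplemental oxygen, by any mode of respiratory support, at the time of randomisation. In section (vi), add that oxygen need is confirmed immediately before the envelope is opened. Keep the existing stop rule. This brings the criterion into line with the Overall Experimental Plan and the Aim 1 titles.

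The primary analysis and the target of 268 do not change. The cost is slightly slower accrual. Section (ix) gives 175 to 200 admissions a year and non-consent below 10%. Taking 10%, and assuming every consenting admission is otherwise eligible, 268 infants take 268 / (200 × 0.9) to 268 / (175 × 0.9) = 1.49 to 1.70 years, or about 18 to 20 months. If the clause removed a further 10%, dividing by 0.9 gives about 20 to 23 months. If few infants are on support without oxygen, the delay is correspondingly small.

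### An infant who reaches Oxygen Index ≥20 after randomisation continues study gas by default with no review called for, although the plan excludes such infants at entry on grounds of harm

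*Combined protocol and SAP*

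**What the plan says.** **Entry.** Research Plan, Specific Aim #1, (iii) Patients admits infants "who are less than 72 hours old, weighing less than 1500 grams at birth, and requiring any respiratory support". Section (iv) then excludes those needing very high ventilatory pressures, defined as an Oxygen Index of 20 or more, and gives a reason: an earlier study "showed that infants in this category are made worse by inhaled nitric oxide".

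**Timing of the check.** Section (vi) places verification before allocation: with the infant "verified to meet inclusion criteria, a sealed envelope containing the randomized treatment assignment" is then opened by the respiratory therapist. No later check of the criterion is described.

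**End of treatment.** Section (vii) Treatment says: "These dosages will continue until the infant no longer needs supplemental oxygen or reaches 33 weeks post conceptional age". The Specific Aims give the same two end points: gas runs until infants are off supplemental oxygen or "reach 33 weeks gestational age, whichever comes first".

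**Monitoring and blinding.** Section (xi) Safety monitoring says that "methemoglobin is regularly monitored with arterial blood gases" and provides one interim safety comparison, of deaths and severe intraventricular hemorrhage, at 50% enrolment. On blinding, (vii) states: "Only respiratory therapy and data safety monitor to know of gas assignments".

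**The concern.** Section (iv) does more than set an entry threshold. It gives a reason, and the reason is harm from the study drug in a defined state of illness. Infants can enter that state after randomisation as well as before it. The treatment rule takes no account of this: it names two end points, and deterioration is neither of them.

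What is at stake is the care of the individual infant. Care is shared by eight neonatologists, and caregivers do not know which gas is running. Without a written prompt, whether anyone reconsiders study gas in a deteriorating infant may depend on who is on duty. The estimate of the treatment effect is not in question here.

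**Working it through.** The plan gives no figure on this point, so there is none to reproduce. The check is to set the provisions side by side and then see what can and cannot be sized.

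**Step 1: does the written rule reach this infant?** Take an infant randomised before 72 hours of age with an Oxygen Index below 20, who later reaches 20 or more before 33 weeks.
- First end point, no further need for supplemental oxygen: not met, since an infant this ill still needs oxygen.
- Second end point, 33 weeks: not met, by assumption.
- Result: under (vii) and the Specific Aims, gas continues.

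**Step 2: does any other provision intervene for that infant?**
- (xi) monitors methemoglobin, with no action level stated and no mention of the Oxygen Index.
- The stopping rule in (xi) halts the whole study for an excess of deaths or severe hemorrhage on iNO. It does not act on one infant.
- (x) Standards of neonatal intensive care leaves ventilatory mode to the clinicians and does not address study gas.
- (xvii) Anticipated results and critique sets the pace of weaning, 1 ppm every 12 to 24 hours, but not a reason to begin it.
- Result: no provision calls for a review.

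**Step 3: is there treatment time in which this could occur?** All study gas is given after the entry check. Specific Aim #2, (ii) Study Design expects every infant born before 31 weeks to be treated for more than 2 weeks. This shows that there is time on gas when the criterion is not looked at again. It does not measure time spent at an Oxygen Index of 20 or more.

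**Step 4: how many infants?** The documents give no rate, so the number cannot be computed. For scale only, take the planned enrolment of 268 in (ix) Sample size and assume an equal split: 268 / 2 = 134 on iNO. The rates below are assumptions with no support in the documents.

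| Assumed rate of a confirmed value | iNO infants |
|---|---|
| 2% | 0.02 × 134 = 2.7, about 3 |
| 5% | 0.05 × 134 = 6.7, about 7 |
| 10% | 0.10 × 134 = 13.4, about 13 |

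If rates were equal, a similar number on placebo would meet the trigger, but they carry no risk from iNO.

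**Step 5: how long would a wean take?** From the 5 ppm ventilated dose, in 1 ppm steps:
- First step immediate: 4 intervals, 4 × 12 to 4 × 24 = 48 to 96 hours.
- First step after one interval: 5 intervals, 5 × 12 to 5 × 24 = 60 to 120 hours.
- Result: about 2 to 5 days. A wean on this schedule is not a prompt stop, which matters for the form of the fix.

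**The case against.** The strongest reply is that an entry criterion and a duration rule do not conflict merely because the first is not repeated in the second. Section (iv) explains why infants already at that level of illness are not enrolled. It does not say that the harm extends to infants who deteriorate while on 5 ppm, and the cited study is not available to settle this. On that view, the plan only lacks detail about individual discontinuation.

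Much of this stands. A reader might infer that the plan obliges staff to keep infants on a gas it regards as harmful. The documents do not support that: nothing forbids a clinician from stopping, and intent-to-treat analysis would retain an infant whose gas ended early. A reader might also infer that gas should stop automatically at the threshold. That is not supported either. Section (xvii) reports that some infants tolerated weaning poorly, and although it calls this a minor complication, it does not discuss weaning during severe respiratory failure. A forced 2-to-5-day wean could be slow and poorly tolerated at once.

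There is also a practical limit. Aim #2 plans arterial as well as venous sampling through week 2 and venous sampling only after that, so arterial gases may be less frequent later. The daily data under (viii), "Clinical data (fluids, medications, diagnoses, ventilator settings) will be collected daily by our research professional", are research records and not a bedside alert.

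What does not fall is the mismatch itself. The treatment rule is stated twice, with two end points, and the plan's own harm statement concerns a state that infants can enter later. If the investigators think that continuing gas differs from starting it, the plan should say so.

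**Conclusion.** The point holds as a patient-safety inconsistency worth a short amendment. By default, study gas continues in an infant who reaches the level of illness that the plan excludes on grounds of harm, and no review is called for.

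Its size is unknown. The documents give neither the frequency of an Oxygen Index of 20 or more after entry nor the harm of continuing, and the counts of 3, 7 and 13 only illustrate assumed rates. A reader might go on to infer bias or a distorted treatment effect; nothing in the documents shows either.

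The conclusion rests on two readings: that (iv) applies at entry only, as its place among the exclusion criteria and the check before the envelope suggest, and that the plan's own account of the earlier study is taken as it stands.

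**What to change.** Add to (vii) Treatment:
- **Trigger.** A confirmed Oxygen Index of 20 or more while ventilated, on arterial gases drawn for clinical care. Confirmed means a repeat value and not a single transient one; the investigators set the interval.
- **Action.** A prompt, documented decision by the treating clinician, still blinded, to continue or to wean study gas. The rule is identical in both arms, and the unblinded data safety monitor does not make the decision for the individual infant.
- **Wean, if chosen.** The schedule in (xvii), or faster if judged necessary, run by the respiratory therapist with a matching sham wean on the shrouded placebo device.
- **Follow-up and reporting.** Keep these infants in intent-to-treat follow-up to 18 months, and give the count by arm to the data safety monitor at the 50% safety look.

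This is a cheap improvement. It needs no extra blood draws, and respiratory therapy already runs the devices. The costs are a little documentation, shorter exposure for a few infants, and possible weaning intolerance. That last risk is why weaning is left to the clinician and is not automatic. Tying the trigger to clinically drawn gases means that it will not detect a crossing when no arterial gas is taken.
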